3.3.1 Inclusion Criteria

Eligible patients will be admitted to an intensive care unit and fulfill the following inclusion criteria:

- i) age \geq 18 years
- ii) patient weight \geq 55 kg
- iii) plan to initiate CRRT or within 24 hours of having started CRRT for AKI
- iv) expected to survive and receive CRRT for a duration of \geq 48 hours
- v) able to provide informed consent or have an authorized representative provide consent after being informed of the details and risks of the trial unless a deferred consent process is approved by the local Research Ethics Board (REB).

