3.4 Interventions

3.4.1 Study Interventions

All enrolled patients will receive the standard dose-intensity for a maximum of 24 hours and a minimum of 12 hours from the time CRRT is started (not the time of enrollment and randomization) to ensure initial metabolic and azotemic stabilization.

The *experimental arm* will be lower CRRT dose-intensity, defined by a delivered effluent flow rate of **10-15 mL/kg/hr**. The rationale for this lower dose-intensity is based on the observed lower threshold currently delivered in clinical practice and observational data showing that this threshold is acceptable, tolerated and safe.[26-28] The *control arm* will be guideline-directed standard CRRT dose-intensity, defined by a delivered effluent flow rate of **25-30 mL/kg/hr**. The standard dose-intensity aligns with current practice and by recommendations from international CPGs.[31] The standard of care for CRRT dose-intensity provided in ICUs in Alberta in a recent audit and across participating sites in STARRT-AKI (39 Canadian sites) ranged between 26-30 mL/kg/hr. The dose calculation will utilize measured or estimated actual body weight.

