3.4.2 Criteria for discontinuing or modifying allocated interventions

The duration of the intervention will be until CRRT is discontinued due to any of patient death, transition to intermittent RRT (IRRT) or due to kidney recovery with no further requirement for RRT. Transition to IRRT will align with current best practices and align with local standards of care. This will generally occur following hemodynamic stabilization and weaning of vasoactive support (i.e., SOFA_{CV} score <2). Ultimate decisions about transitions to IRRT will be made by the local attending physicians. If during their ICU admission a patient has their CRRT temporarily interrupted (e.g., diagnostic imaging or other investigations; procedures or operations), once restarted, the CRRT will be prescribed according to their allocated dose-intensity. If a patient has prolonged CRRT interruption (>6 hours) (e.g., operative theatre), CRRT will be temporarily restarted at the standard dose-intensity for 6 hours to ensure a period of stabilization, then transitioned to their allocated CRRT dose-intensity, as applicable.

If patients are perceived by the treating ICU team to require a temporary increase in dose-intensity to augment acid-base/metabolic/azotemic control due to critical illness, the following actions should be followed in hierarchical order:

- i) For patients with persistent hyperkalemia, defined as [K+] > 5.5 mmol/L at 24 hours after randomization, the treating ICU team can lower the potassium [K+] concentration in the replacement/dialysis solutions, as per ICU-specific protocols.

- ii) For patients with persistent metabolic acidosis, defined as pH <7.25 and BE < -10 at 24 hours after randomization, the treating ICU team can add supplementary bicarbonate (HCO₃) either as a continuous infusion or bicarbonate can be added to the replacement/dialysate solutions, as per ICU-specific protocols.
- iii) For patients who are refractory to the above modifications to the prescribed CRRT or those who have persistent azotemia, defined as [urea] >30 mmol/L at 24 hours after randomization, the treating ICU team can adjust the dose-intensity to the upper limit of dose-intensity within the allocation. For example, in those patients allocated to the low dose-intensity group (target 10 mL/kg/hr), adjust the prescribed dose to 15 mL/kg/hr.

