If patients have their CRRT dose-intensity prescription further modified outside their allocated dose-intensity (e.g., a patient allocated to 10-15 mL/kg/hr is increased to >15 mL/kg/hr) for reasons not specified above, this will be considered a protocol deviation. The reason for the dose-intensity modification must be documented and will be classified as: i) inadequate acid-base control; ii) inadequate electrolyte control; iii) inadequate azotemic/metabolic control; and iv) other (describe).

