3.5.2 Secondary Endpoints

The secondary feasibility endpoints are:

- i) Ability to enroll an average of 2 patients per site per month. We believe a target of 2 per month is feasible across sites in Alberta given the number of patients starting CRRT per month (~32 new CRRT initiations per month) and accrual at sites during the STARRT-AKI trial.
- ii) The ability to enroll >50% of fully eligible patients.
- iii) Time from eligibility (e.g., starting RRT) to randomization with a target of >75% of eligible patients within 12 hours.
- iv) Protocol adherence for allocated CRRT dose-intensity. We believe a target in-range dose-intensity of >80% to be adequate.
- v) Ability to capture delivered CRRT dose-intensity measures. This is a process measure of trial implementation and fidelity. We believe a target of electronic capturing >95% of daily time-averaged CRRT dose-intensity data to be adequate. This will enable an assessment of difference in CRRT dose-intensity between groups.
- vi) Ability to capture patient and kidney endpoints at 90-days from randomization. We believe a target of >95% ascertainment to be adequate.

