3.5.4 Process of Care Endpoints

The process of care measures will assess the tolerability of the intervention and are:

- i) The lowest and highest CRRT dose-intensity delivered for any given hour following randomization.
- ii) The proportion of hours of CRRT when the dose-intensity is in the target range following randomization.
- iii) The total treatment time/day while receiving CRRT following randomization. This will be defined as time on treatment divided by 24-hours.
- iv) The total number of hemofilter/circuit replacements during CRRT following randomization.

- v) The total volume of replacement/dialysate fluid used per day and overall following randomization.
- vi) The total number and cumulative doses of supplemental electrolytes (Mg⁺, K⁺, PO₄⁻, HCO₃⁻), protein and vitamins administered while receiving CRRT following randomization.
- vii) The modified daily bedside (nursing) activity score, as a measure of nursing bedside workload, while receiving CRRT following randomization.
- viii) The mean daily net ultrafiltration (UF_{NET}) delivery while receiving CRRT following randomization.

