7.4 Protocol Deviations

A protocol deviation is any noncompliance with the clinical trial protocol, International Conference on Harmonisation Good Clinical Practice (ICH GCP), or Manual of Procedures (MOP) requirements. The noncompliance may be either on the part of the participant, the investigator, or the study site staff. As a result of deviations, corrective actions may need to be developed by the site and implemented promptly.

These practices are consistent with ICH GCP E6 (R2):

- 4.5 Compliance with Protocol, sections 4.5.1, 4.5.2, and 4.5.3
- 5.1 Quality Assurance and Quality Control, section 5.1.1
- 5.20 Noncompliance, sections 5.20.1, and 5.20.2.

It is the responsibility of the site investigator to use continuous vigilance to identify and report deviations. All deviations must be addressed in the source documents and reported in the participant database as soon as the study team is aware of the deviation. Protocol deviations must be sent to the local REB per their policies. The site investigator is responsible for knowing and adhering to the reviewing REB requirements.

Examples of protocol deviations which may occur (but are not limited to) include:

- Consent Procedures error: no consent/re-consent obtained (deferred, SDM/participant or regained capacity), incorrect consent form used, not all signatures obtained, etc
- Inclusion/Exclusion criteria not met
- Study Procedures: did not begin receiving study-prescribed CRRT within the protocol specified timelines, received incorrect CRRT prescription, CRRT dose escalated above the protocol-mandated dose-intensity target
- Confidentiality Breach
- SAE Reporting: Did not notify coordinating centre of SAE within 24 hours of becoming aware

There may be other types of deviations that occur as well. All deviations should be recorded in the REDCap participant database. Further details about the handling of protocol deviations are included in the MOP.

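### In-range hours are counted from randomization but the run-in is timed from CRRT start, so compliant standard-dose hours score against the low arm only

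*Protocol*

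**What the plan says.** Section 3.5.4 ii defines the only in-range measure in the protocol: "The proportion of hours of CRRT when the dose-intensity is in the target range following randomization". It makes no exception for any hours.

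Section 3.4.1 gives every enrolled patient the standard dose for "a maximum of 24 hours and a minimum of 12 hours from the time CRRT is started (not the time of enrollment and randomization"). The low-arm range is 10-15 mL/kg/hr. The control range is 25-30 mL/kg/hr, which is also the run-in dose.

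Two provisions put randomization early on that clock. Section 3.3.1 iii admits patients with a "plan to initiate CRRT or within 24 hours of having started CRRT for AKI", so randomization can precede CRRT. Section 3.5.2 iii sets as a feasibility target "Time from eligibility (e.g., starting RRT) to randomization with a target of >75% of eligible patients within 12 hours".

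Section 3.4.2 adds a second block. After an interruption of more than 6 hours, "CRRT will be temporarily restarted at the standard dose-intensity for 6 hours to ensure a period of stabilization".

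The protocol treats these hours as compliant. In 3.4.2 a dose outside the allocation is a deviation when it occurs "for reasons not specified above, this will be considered a protocol deviation". In 7.4 a late start is a deviation when the patient "did not begin receiving study-prescribed CRRT within the protocol specified timelines".

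Section 3.5.2 iv reads: "Protocol adherence for allocated CRRT dose-intensity. We believe a target in-range dose-intensity of >80% to be adequate". It gives no counting window and does not refer to 3.5.4 ii.

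**The concern.** The counting window opens at randomization, but the low dose may not start before CRRT hour 12 and need not start before hour 24. For a patient randomized before the switch, the hours in between are at the standard dose because 3.4.1 requires it (to hour 12) or permits it (to hour 24). The same care counts as a miss in one arm and a hit in the other.

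The pilot exists to learn whether the low dose can be delivered and kept apart from the standard dose. A measure that understates delivery in the low arm alone can make a workable intervention look poorly delivered. The understatement grows with faster randomization and shorter CRRT, so doing well on the time-to-randomization target lowers the low arm's in-range score.

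**Working it through.** **Inputs from the protocol**
- CRRT duration (2.3): 2,790 CRRT-days in 518 patients. 2,790 / 518 = 5.39 days, which reproduces the stated average of 5.4. In hours, 5.386 × 24 = 129.3.
- Run-in (3.4.1): switch to the low dose at hour *s* from CRRT start, 12 ≤ *s* ≤ 24.
- Randomization (3.3.1, 3.5.2 iii): hour *r* from CRRT start, taken as 0 if before CRRT, up to 24, with a target of more than 75% within 12 hours.

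**Assumptions, not in the protocol**
- 75% randomized evenly over hours 0-12 and 25% evenly over hours 12-24.
- Switch evenly over hours 12-24, with all at hour 12 and all at hour 24 as the extremes.
- Run-in hours are delivered within 25-30 mL/kg/hr when the protocol is followed.

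**One fully compliant low-arm patient**

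Highest possible score = (T − max(r, s)) / (T − r), where T is total CRRT hours. A compliant control patient scores 100% in every row.

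| r | s | T = 48 h | T = 72 h | T = 129.3 h |
|---|---|---|---|---|
| 6 | 12 | 36/42 = 85.7% | 60/66 = 90.9% | 117.3/123.3 = 95.1% |
| 0 | 12 | 36/48 = 75.0% | 60/72 = 83.3% | 117.3/129.3 = 90.7% |
| 6 | 24 | 24/42 = 57.1% | 48/66 = 72.7% | 105.3/123.3 = 85.4% |

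The score is below 80% when T < r + 5(s − r). For r = 6 that is T < 36, 66 and 96 h at s = 12, 18 and 24. Inclusion iv requires only an expected CRRT duration of at least 48 hours, so shorter courses will occur: r = 6, s = 12, T = 30 gives 18/24 = 75%.

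**The whole low arm, hours pooled**

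- Mean r = 0.75 × 6 + 0.25 × 18 = 9 h, so mean CRRT after randomization = 129.3 − 9 = 120.3 h.
- Mean standard-dose hours after randomization, E[max(0, s − r)]:
  - s even over 12-24: 0.75 × (18 − 6) + 0.25 × (12/6) = 9.5 h. For two independent uniform times on the same 12-hour interval the mean positive difference is 12/6 = 2 h.
  - all at 12: 0.75 × 6 = 4.5 h.
  - all at 24: 0.75 × 18 + 0.25 × 6 = 15.0 h.

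| | s even over 12-24 | all at 12 | all at 24 |
|---|---|---|---|
| Low-arm ceiling (1 − hours/120.3) | 92.1% | 96.3% | 87.5% |
| Control-arm ceiling | 100% | 100% | 100% |
| Low arm shows, if 85% in range after the switch | 78.3% | 81.8% | 74.4% |
| False gap to a control arm at 85% | 6.7 points | 3.2 | 10.6 |
| Mean of both arms | 81.6% | 83.4% | 79.7% |

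**Sensitivity to randomization time.** If all are randomized evenly over hours 0-12, the ceilings are 90.3%, 95.1% and 85.4%. If all are randomized evenly over hours 0-24, they are 94.0%, 97.4% and 89.8%.

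**Restarts.** One 6-hour restart costs 6/120.3 = 5.0 points. If every low-arm patient had one (assumed; range 0 to 1), the base ceiling falls from 92.1% to 87.1%.

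**The case against.** Section 3.5.4 describes care as delivered, and low-arm patients really did receive the standard dose in these hours. Counting from randomization is a usual description of exposure. The protocol does not say hour by hour what the target range is; read as the dose prescribed at that hour, the arms are treated alike. How 3.5.2 iv is scored (hours, days or patients, by arm or overall) is ordinary material for a statistical analysis plan, and 3.5.2 v mentions daily time-averaged doses, which could be its basis instead.

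Part of this stands. The link from 3.5.4 ii to the >80% target is an inference: 3.5.4 ii is the only in-range measure defined, but the current text does not call it the adherence measure. The missing window in 3.5.2 iv is not itself a fault. A count over all hours is also worth keeping as a description of exposure.

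The rest does not answer the point. Section 3.5.4 ii does fix its window, at randomization and without exception. The only ranges the protocol defines are those of the allocated arms, so scoring against the allocation is the natural reading. The result is a stated rule that treats identical compliant care differently by arm.

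A reader might go further in three ways that the documents do not support.
- *The low arm cannot reach 80%.* With no restarts, every pooled ceiling above exceeds 80%. An arm that delivers well after the switch may read as short of the target, but the target remains attainable.
- *The pilot would be stopped wrongly.* No go/no-go rule is attached to >80%.
- *The primary endpoint is diluted in the same way.* Section 3.5.1 states no counting window for the delivered dose, so nothing in the text establishes this.

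**Conclusion.** The point holds for the in-range measure in 3.5.4 ii, read against the allocated range. Hours at standard dose that the protocol requires or permits after randomization lower the low arm's score and leave the control arm's untouched. The direction needs only that some low-arm patients are randomized before their switch, or have a restart after a long interruption; the protocol's own time-to-randomization target makes the former the usual case.

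The size rests on assumed randomization and switch times, and on a mean duration taken from all Alberta CRRT patients, of whom an estimated 77% had AKI. It should be read as illustrative. The consequence is a feasibility result that could be misread. The defect is worth correcting because the correction is cheap, but it does not undermine the trial.

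**What to change.** Amend 3.5.4 ii so that each CRRT hour after randomization is scored against the dose the protocol prescribes for that hour, and report it by arm:
- 25-30 mL/kg/hr during the run-in: in the low arm until the switch to the low dose, no earlier than hour 12 and no later than hour 24 from CRRT start;
- 25-30 mL/kg/hr during the 6-hour restart after an interruption of more than 6 hours;
- the allocated range in all other hours.

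State in 3.5.2 iv that the >80% target uses this measure. Beside it, report the share of all post-randomization CRRT hours in the allocated range, as a description of exposure.

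A fully compliant patient then scores 100% in either arm, and a true 85% in both arms shows as 85% in both. Opening the window at hour 24 in both arms would also restore balance, but it would drop up to 12 compliant low-dose hours per patient and all patients who stop CRRT before hour 24. Scoring by prescribed dose loses neither.

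The cost is a few sentences, with no extra patients or tests. The switch time must be derived from the hourly dose data that 3.5.4 already needs. Low-arm run-in hours at standard dose will count as adherent, so a late but permitted switch does not show in the adherence figure; this is why the exposure description has to stand beside it.

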3.5.5 Safety

An adverse event (AE) is any untoward medical occurrence in a patient enrolled in the trial which does not necessarily have a causal relationship with the intervention. A serious adverse event (SAE) is defined as any untoward medical occurrence that results in death, is life-threatening, requires hospitalization (overnight or longer), causes prolongation of existing hospitalization, results in persistent or significant disability or incapacity; results in congenital anomaly or birth defect; other medically important event (is not immediately life-threatening or results in death or hospitalization but may jeopardize the subject or require intervention to prevent one of the above outcomes). Due to this trial being performed in critically ill patients, AEs and SAEs are expected to occur frequently. As such, AE and SAE reporting will follow recommendations set out for trials in this population by Cook and colleagues.[32] This includes a predefined list of AEs that will be considered potentially trial-related AEs and require reporting in the REDCap database. SAEs will be graded based on Common Terminology Criteria for Adverse Events (CTCAE) (grade 1-5) and assigned causality with the intervention (definite, probable, possible or unlikely related).[33] Information related to the trial-related SAEs will be captured on a dedicated form, shared with the study sponsor and submitted to the REB, as applicable (See the Manual of Procedures (MOP) for details of the predefined AEs and recording and reporting requirements for trial-related AEs and SAEs).

Table. Summary of predefined adverse events that will be considered potentially trial-related.

Adverse Event	Definition
Serum K⁺	<3.0 or >6.0 mmol/L
Serum Mg⁺	<0.5 or >1.5 mmol/L
Serum PO₄⁺	<0.5 or >2.5 mmol/L
Serum Urea	>35 mmol (24 hour after randomization)
Serum pH	<7.20 or >7.60 mmol/L
Serum HCO₃	<10 or >35 mmol/L
Serum Ionized Ca⁺	<0.80 or >1.50 mmol/L

Generalized Seizures	Occurrence of a generalized seizure
Arrhythmias	New atrial fibrillation or occurrence of ventricular tachycardia or fibrillation (As defined in STARRT-AKI)
Major bleeding	Major Bleeding will be classified as “major” if it was: 
 • Life threatening bleeding due to hypovolemic shock (e.g., ruptured AAA or upper or lower GI hemorrhage); • Life threatening bleeding at a critical site (e.g., intracranial, retroperitoneal, pericardial); • Overt, clinically important bleeding associated with one of the following within 24 hours of the bleed: decrease in Hgb > 20g/L or transfusion >2 units of packed RBC; • Bleeding at other critical sites (e.g., epidural, intraocular or intraarticular); • Bleeding requiring an invasive intervention (e.g., re-operation).

The safety outcomes reported in REDCap will include:

- i) occurrence of trial-related adverse and serious adverse events
- ii) occurrence of trial-related adverse events and serious adverse events leading to discontinuation of the trial intervention.

3.5.6 Tertiary Endpoints

The WISDOM pilot trial is not designed to detect differences in patient-centred, kidney-centred or health service-specific outcomes[34], however, the following endpoints will be described: duration of RRT; transition from CRRT to IRRT; receipt of RRT at hospital discharge, 30-days and 90-days; RRT-free days at 90-days; ICU mortality; hospital mortality; 90-day mortality; a composite of major adverse kidney events (MAKE) at 30-days and 90-days; change in estimated glomerular filtration rate (baseline to 90-days); daily receipt of non-renal organ support (e.g., invasive and non-invasive mechanical ventilation; vasoactive therapy), ICU duration of stay, hospital duration of stay and re-hospitalization within 90-days. The kidney-specific outcomes, duration of hospitalization, and rates of re-hospitalization are outcomes that have been informed through patient and family preferences and priorities during engagement in our Dialyzing Wisely program.[30] For the next phase trial, the preferable patient-centred primary non-inferiority outcome

will be 90-day mortality (from enrollment) and for superiority, will be RRT-free days at 90-days (from enrollment). These outcomes will aid in the design of a larger-scale trial.

3.6 Sample size calculation and recruitment

For the WISDOM pilot trial, our primary sample size consideration will address the detection of a minimum difference in the delivered dose-intensity of CRRT between the groups. For the WISDOM pilot trial, we are targeting a total sample size of 100 patients (50 patients per group). This is based on the ability to detect a minimum difference of 10 mL/kg/hr in dose-intensity, assuming delivery of 25 mL/kg/hr in the standard dose-intensity group and 15 mL/kg/hr in the lower dose-intensity group, with a conservative standard deviation (SD) of 15, 90% power, and an alpha of 0.05. This would translate into a sample of 96 patients (48 patients per group) that will be inflated to 100 to account for any withdrawal or dropout (See Table below).

Table. Sample Size Calculation Estimates.

Scenario	Difference in Dose Intensity	Standard Deviation	Power	Estimated Sample (Total)
1	10	5.0	0.9	12
2	10	7.5	0.9	24
3	10	10.0	0.9	44
4	10	12.5	0.9	66
5	10	15.0	0.9	96
6 (ATN Trial)	15	6.3*	0.9	18
7 (RENAL Trial)	15	15.3**	0.9	100
* From the ATN trial, based on average standard deviation for both groups of the aggregate total effluent flow rate delivered.[18]				
** From the RENAL trial, based on average standard deviation for both groups of the aggregate total effluent flow rate delivered.[17]				

For the WISDOM pilot trial, the total sample of 100 patients would translate into a target recruitment of 4 patients per week (50% of expected eligible) across 5-10 sites, thereby requiring an estimated 6-10 months to complete, if all sites are active.

We will further explore the practicality of identification of eligible patients, site-specific recruitment, protocol adherence, and data monitoring and ascertainment, that will inform the logistical planning and operations of a larger-scale multi-centre trial.[34]

All patients enrolled in the trial will be admitted to and monitored in an ICU setting. The primary and secondary feasibility endpoints, along with biochemical and process of care endpoints will be captured in local hospital medical records (either paper charts or electronic medical records) and data repositories. Data will be captured electronically where feasible, otherwise, standardized paper case report forms will be used. The expected rate of loss to follow-up will be low for ICU and hospital-specific outcomes

(<1%). Similarly, established processes for linkage to health administrative data ensure longer-term outcomes will be reliably captured.

The WISDOM pilot trial will maintain a screening log to record numbers of patients screened and those eligible and not randomized (e.g., missed, no consent, clinician exclusion), along with the reasons for exclusion. To monitor for selection bias, we will capture a minimal dataset on eligible not randomized patients, as permitted by local REB.[10, 35]

